10.3 Sample Size and Accrual

We expect that it will take 24 months to collect data on all patients through Day 90. Assuming a placebo effect of 30%, we would anticipate a true difference of 1.5 VAS units between the two groups. A true difference between scores of 4.1 to 2.6 would be clinically significant since it would bring a patient from the "moderate" down into the "mild" pain category. Thus a total of 70 patients will enter this placebo-control parallel-design study. The probability is 90 percent that the study will detect a treatment difference at a two-sided 0.05 significance level. This is based on the assumption that the standard deviation of the response variable is 2.5.

10.4 Interim Analyses for Efficacy.

A total of two interim analyses for efficacy will occur after the enrollment of 28 (40%) and 42 (60%) patients, giving a total of 3 'looks' at the data including the final analysis at 70 patients enrolled. Because of the small sample size in the first and second interim analyses, we will test for the equality of static pain scores at 6 hours post-surgery by treatment group using the Wilcoxon rank sum test. This statistical test considers the rank of the pain scores without regard to the distribution of these outcome measures; however, the test of significance uses a Z-score, which has a standard normal distribution.

In order to control for the overall type I error for the three proposed analyses, we will use a group sequential approach that utilizes the O'Brien-Fleming (1979)²⁷ alpha spending function. The critical Z-values for the Wilcoxon rank sum test assuming O'Brien-Fleming boundaries were determined by the STATA command 'landemets', which calculates these boundaries following the method of Lan and DeMets (1983)²⁸. Table X below gives the critical Z values and corresponding alpha levels at each analysis required to reject the null hypotheses of equality of pain scores by treatment group. In this null hypothesis, we consider a two-sided test which makes no assumption about the direction of the effect (e.g. placebo patients could potentially have a lower mean pain score than those on the intervention).

Table 5: Critical Z values and corresponding alpha levels for test the null hypothesis that static 6 hour post-surgery pain scores are equal among treatment groups.

Analysis number	Proportion of total N	critical Z to reject H0	Alpha(i) level
1	0.4	3.36	0.00079
2	0.6	2.68	0.0076
3	1.0	1.98	0.05

References

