APPENDIX E: RAND-36 ITEM SHORT FORM SURVEY	50
APPENDIX F: QUICK DASH QUESTIONNAIRE	54

List of Abbreviations

[figure not shown]
ADR	Adverse Drug Reaction
AE	Adverse Event/Adverse Experience
cc	Cubic Centimeter
CNS	Central Nervous System
CRF	Case Report Form
DASH	Disability of the Arm, Shoulder, and Hand
DATA	Device and Technique Assessment
DIEP	Deep Inferior Epigastric Perforator
HIPAA	Health Information Portability and Accountability Act
ICH	International Conference on Harmonization
ID	Identification
IRB	Institutional Review Board
IV	Intravenous
mg	Milligram
mL	Milliliter
PCA	Patient-Controlled Analgesia
PO	By Mouth (Latin: Per os)
POE	Provider Order Entry (System)
PSEF	Plastic Surgery Education Foundation
PSI	Pounds per Square Inch
RAND	Research and Development
SAE	Serious Adverse Event
SEER	Surveillance, Epidemiology, and End Results
TRAM	Transverse Rectus Abdominus Myocutaneous

1. Protocol Summary

Full Title	Use of Pre-operative Paravertebral Blocks to Decrease Post-operative Pain Following Mastectomy with Immediate Tissue Expander Reconstruction
Short Title	Paravertebral Blocks to Decrease Breast Reconstruction Pain
Study Type	Prospective, Randomized, Double-Blind Clinical Trial
Conducted By	The Department of Plastic and Reconstructive Surgery Johns Hopkins University School of Medicine
Principal Investigator	[name].
Sample Size	Enrolled: 70 (Randomization Treatment: Placebo = 35:35)
Study Population	
 • Women aged 18-75 years. • Choose bilateral mastectomy followed by immediate tissue expander breast reconstruction. • Have no inflammatory breast cancers. • Be aware of the nature of her malignancy. • Understand the study purpose, requirements, and risks. • Be able and willing to give informed consent.
Accrual Period	Two Years

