9.8 Monitoring

The principal investigator will have sole responsibility for monitoring and oversight of problems/events related to this research.

10. Statistical Considerations

This study is a randomized controlled trial based on the bilateral mastectomy followed by bilateral immediate tissue expander breast reconstruction surgical protocol currently in use at Johns Hopkins.

Patients will be randomized 1:1 to either 0.5% ropivacaine pre-operatively placed paravertebral blocks or subcutaneous paravertebral saline (placebo) injections. Using two pain scales, the Patient Pain Assessment Questionnaire (Appendix A) and Subjective Pain Survey (Appendix B), the post-operative pain will be compared between treatment and control groups. Differences in opioids use between groups at different time points will also be assessed as a more objective measure of post-operative pain.

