10.2 Study Design

Descriptive statistics for all outcome data (primary, secondary, and tertiary) will be calculated for each treatment group (ropivacaine or placebo), for each time point (days 1-3, day 90, year 2 and year 4). Student's t-test or Wilcoxon rank sum test will be used to compare the 2 treatment groups with regards to continuous or ordinal (approximately continuous) data, based on the distribution of the values (normally distributed or not normally distributed). Also change from baseline to each time point (follow-up) will be calculated for each outcome. The distributions of these "change values" will be analyzed in the same manner (depending on distribution). P-values less than 0.05 will be considered statistically significant for the primary outcome.

Longitudinal methods will be used to examine trends in scores, and changes in scores over time.

Opioid use also will be analyzed. IV morphine delivered via a Patient Controlled Analgesia pump during the first 24 hours of post-operative hospitalization will be recorded. Oxycodone and Tylenol taken by the patient after the first 24 hours until post-operative day seven will be recorded by the patient unless the patient is still hospitalized, in which case it will be recorded in the patient's medical record and abstracted by study staff. Answers to pain questionnaires and information regarding analgesic use will be verified by daily telephone calls to the patients by study staff. A common "pain unit" will be developed to standardize the various methods of opioid administration. Survival analyses will be used to compare time to opioid use, and time to stopping of opioid use. Descriptive statistics will be used to quantify amount and timing of opioid use, as well as proportion of patients requiring opioids post-operatively.

Furthermore, we will use the DASH survey, BREAST-Q[®], and the RAND-36 to determine the amount of functional long-term differences (3 months, 2 and 4 years after surgery) between treatment groups. These surveys will be used to compare the functional use of the arm before surgery to its use three months after mastectomy with immediate reconstruction.

Adverse events will be quantified and proportions of patients in each treatment group with different specific types of adverse events will be compared for safety data. Chi Square tests or Fisher's Exact Tests will be used to compare the proportions of patients with adverse events.

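### Section 10.3 claims 90% power, but its own inputs (35 per arm, difference 1.5, SD 2.5, two-sided 0.05) give about 70%

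*Combined protocol and SAP*

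**What the plan says.** All the inputs are in the combined protocol and SAP.

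- **Sample size and design.** Section 10.3: "Thus a total of 70 patients will enter this placebo-control parallel-design study".
- **Allocation.** The Protocol Summary (Section 1) gives "Enrolled: 70 (Randomization Treatment: Placebo = 35:35", and the opening of Section 10 confirms it: "Patients will be randomized 1:1 to either 0.5% ropivacaine pre-operatively placed paravertebral blocks".
- **Difference.** Section 10.3: "we would anticipate a true difference of 1.5 VAS units between the two groups". The same paragraph gives it again as two scores: "A true difference between scores of 4.1 to 2.6 would be clinically significant".
- **Variability.** Section 10.3: "This is based on the assumption that the standard deviation of the response variable is 2.5".
- **Claimed power and alpha.** Section 10.3: "The probability is 90 percent that the study will detect a treatment difference at a two-sided 0.05 significance level".
- **Test.** Section 10.2 leaves the choice open, depending on the distribution: "t-test or Wilcoxon rank sum test will be used to compare the 2 treatment groups". No covariate adjustment is specified.
- **Looks.** Section 10.4 adds interim efficacy analyses at 28 and 42 patients, with critical Z values of 3.36, 2.68 and 1.98 (Table 5).

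Section 10.3 states no dropout allowance.

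**The concern.** A difference of 1.5 against a standard deviation of 2.5 is a standardised effect of 0.6. Thirty-five patients per arm is too few for 90% power at that effect size with a two-sided 0.05 test. Sample size, standard deviation, difference and power in Section 10.3 therefore cannot all be right.

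This paragraph is the only justification for the sample size on the primary endpoint. A reader who trusts the 90% would take a non-significant result as fairly strong evidence against a 1.5-point benefit. A null result is a realistic possibility, since the Rationale itself cites two randomised mastectomy trials that found no benefit from paravertebral block.

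**Working it through.** **Inputs.** n = 35 per arm (Section 1); difference 1.5, with 4.1 − 2.6 = 1.5 as a check; SD 2.5; two-sided alpha 0.05 (Section 10.3).

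**Step 1. Power from the stated inputs.**

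- Standard error of the difference: 2.5 × √(2/35) = 0.598.
- Normal approximation: 1.5/0.598 = 2.51, and Φ(2.51 − 1.96) = Φ(0.55) = **0.709**.
- Two-sample t-test (noncentral t, 68 degrees of freedom, noncentrality 2.51): **0.697**.

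The stated 0.90 is not reproduced.

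**Step 2. What 90% power would need.**

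| Quantity changed, others held | Normal approximation | t-test |
|---|---|---|
| Patients per arm | 2 × (1.96 + 1.2816)² × 2.5²/1.5² = 58.4, so 59 | 59.4, so 60 (power 0.903) |
| Difference | (1.96 + 1.2816) × 0.598 = 1.94 | 1.97 |
| SD | 1.5/[(1.96 + 1.2816) × √(2/35)] = 1.94 | 1.91 |

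On the t-test figure the total is 120, which is 120/70 − 1 = 71% more than planned. With 35 per arm and SD 2.5, the t-test detects 1.70 points at 80% power.

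**Step 3. Other readings that might recover 90%.**

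| Reading | Result |
|---|---|
| One-sided 0.05 | 80.0% (t), 80.7% (normal) |
| 70 patients per arm | 94.1% (t), 94.4% (normal) |
| Difference before a 30% placebo discount, 1.5/0.7 = 2.14 | 94.2% (t), 94.8% (normal) |
| One-sample, n = 35 | 94.4% (normal) |
| Paired or crossover | 90% needs about 30 or 58 patients, not 70 |
| Wilcoxon at relative efficiency 0.955 | 68.9% (normal) |

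None returns 90%. The one-sided, per-arm, one-sample, paired and crossover readings also contradict the plan's text.

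**Step 4. The three-look design.** This was simulated with 14, 21 and 35 per arm, interim Wilcoxon tests at |Z| > 3.36 and 2.68, the final test at the 1.98 level, means 4.1 and 2.6, and SD 2.5. The score distributions are assumptions, because the plan gives none.

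| Assumed scores | Final t-test | Final Wilcoxon |
|---|---|---|
| Normal (200,000 runs) | 0.692 | 0.667 |
| Truncated normal, rounded to 0–10 (40,000 runs) | 0.674 | 0.653 |
| Beta, rounded to 0–10 (20,000 runs) | not run | 0.75 |
| Gamma, skewed (200,000 runs) | 0.715 | 0.870 |

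The looks cost very little power, and no scenario reaches 0.90.

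**Step 5. Reading a null result.** The expected 95% confidence interval half-width is t(68) × 0.598 = 1.19 points. The interval excludes 1.5 only if the observed difference is below 1.5 − 1.193 = 0.307, about 0.31.

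**The case against.** The arithmetic is not in dispute, but four points can be made against the conclusion drawn from it.

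1. **Which figure is wrong is not shown.** The power sentence names no size of difference. Read alone, it is consistent with 70 patients and SD 2.5 if the difference were 1.97. But 1.5 is the only difference in the paragraph, it is given in two forms, and the sample size is presented as following from it. The 90% is therefore wrong for the difference the plan uses. The sponsor may still have meant a different SD or difference, and the fix allows for that.

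2. **About 70% is a t-test or normal-score figure.** A normal score with mean 2.6 and SD 2.5 puts about 15% of patients below zero on a 0–10 scale, so non-normal scores are plausible, and Section 10.4 describes the Table 5 boundaries as Wilcoxon critical values. With a final Wilcoxon test, simulated power ran from 0.65 to 0.87 across the assumed distributions. This stands as a limit on precision: the 70% should be quoted with its test. It does not rescue the 90%.

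3. **Baseline adjustment could raise power.** Reaching 90% that way would take a baseline correlation of about 0.63. The plan states no correlation and its test is unadjusted.

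4. **Keeping 70 patients is a preference.** The looks are also given as 40% and 60% of the total and could scale with a larger trial. That is fair: whether about 70% power is acceptable is for the sponsor to decide.

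**Conclusion.** The concern holds. On the plan's own inputs, power to detect 1.5 points is 69.7% by two-sample t-test (70.9% by normal approximation) against a stated 90%. The type II error is about 30%, three times the implied 10%. This assumes SD 2.5, a true difference of 1.5 and all 70 patients evaluable. As an illustration only, a 10% loss (31.5 per arm) would lower the normal-approximation power to about 66%. With a final Wilcoxon test the type II error ranged from about 13% to 35% under the distributions tried, and none of these gave 90% power. The error does not invalidate the trial, but it overstates what a non-significant result would mean.

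**What to change.** Keep 70 patients and correct the power statement in Section 10.3. Suggested text:

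> *With 35 evaluable patients per arm, a two-sample t-test at the two-sided 0.05 level has about 70% power for a 1.5-point difference if the SD is 2.5. Power of 90% applies only to a difference of about 2.0 points.*

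If a different SD or difference was intended, state and justify it so that sample size, SD, difference and power agree. Any power quoted for the Wilcoxon test or the three-look design should name its score distribution and final test. Add that a non-significant primary result will be interpreted by its confidence interval against 1.5 points.

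The cost is a wording amendment and a less favourable stated power, with no extra patients. Seventy is the practical choice because the 35:35 allocation, the looks at 28, 42 and 70, and the two-year accrual are built on it. The alternative is 120 patients, which at the same rate takes 24 × 120/70 = 41 months. If the 24 months in Section 10.3 includes about three months of follow-up to Day 90, it takes about 21 × 120/70 + 3 = 39 months.

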5.6 Blinding

Both patients and the treating anesthesiologist(s) will be blinded as to whether the patients are receiving a ropivacaine (treatment) or saline (placebo) solution through the Day 90 visit. One anesthesiologist (who is also a co-investigator), which will not be involved with the intra- and postoperative patient care and data collection, will perform all the paravertebral blocks and sham procedures. The anesthesiologists managing intra- and postoperative patient care and all data collection will be unaware of the group assignment. Postoperative assessments will be performed by anesthesiologists who will be blinded to each patient's group. This strategy will allow a double-blinded design. Blinding the study will help to reduce the chance of bias in subjective outcomes such as pain scores and quality-of-life scores. Once all enrolled patients have completed their Day 90 visit, unblinding will occur for study staff to enable data analysis. Patients will have the option of learning their treatment assignment group once they have completed their Year 4 follow-up interview.

In case of an emergency when the treating investigator deems identification of the study drug necessary for the purpose of providing urgent patient care, and knowledge of the subject's treatment assignment will alter subsequent care, then the investigator is authorized to break the blind. In order to learn of the randomization assignment, the Principal Investigator or designee will contact the Research Pharmacy to request treatment assignment information.

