9.5 Data and Safety Monitoring

This is a DSMP Level I study under the SKCCC Data Safety Monitoring Plan. The Clinical Research Office QA Group will perform an audit at the end of the first year and then periodically depending on the rate of accrual and prior audit results. The SKCCC Safety Monitoring Committee will review all trial monitoring and reporting annually. The PI will be responsible for monitoring the study. The study's data will be continuously reviewed to assure its validity. The PI will constantly review the safety reports to confirm that the safety outcomes favor continuation of the study. Additionally, the PI will be responsible for maintaining the clinical protocol, monitoring clinical trial efficacy endpoints, reporting adverse events, assuring that consent is obtained and documented, reporting of unexpected outcomes, and reporting the status of the trial in the continuing renewal report submitted to the IRB and to the trial monitoring review group.

Content of the continuing renewal report at a minimum will include year-to-date and full trial data on: accrual and eligibility, protocol compliance, treatment administration, toxicity and ADR reports, response, survival, regulatory compliance and compliance with prearranged statistical goals. The report will be submitted in a timely manner according to the schedule defined by Johns Hopkins Medicine Institutional Review Board.

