9.7 Safety Meetings

Scheduled meetings will take place as needed and will include the protocol principal investigator, study coordinator(s), sub-investigators (as appropriate), and biostatisticians (as appropriate) involved with the conduct of the protocol. During these meetings matters related to the following will be discussed: safety of protocol participants, validity and integrity of the data, enrollment rate relative to expectation, characteristics of participants, retention of participants,

adherence to the protocol (i.e., potential or real protocol deviations/violations), completeness of data collection, and progress of data analysis.

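### The two interim comparisons by treatment group fall well before section 5.6 allows unblinding for analysis, and no one is named to run them, receive them or keep them from the study team

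*Combined protocol and SAP*

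**What the plan says.** On the looks, section 10.4 states: "A total of two interim analyses for efficacy will occur after the enrollment of 28 (40%) and 42 (60%) patients". It then specifies the comparison: "we will test for the equality of static pain scores at 6 hours post-surgery by treatment group using the Wilcoxon rank sum test". Table 5 gives the boundary for each look and for the final analysis.

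On the blind, section 5.6 states: "Once all enrolled patients have completed their Day 90 visit, unblinding will occur for study staff to enable data analysis". Its only exception is emergency care, for which the PI or a designee asks the Research Pharmacy for the assignment. Section 5.7 keeps the study team blinded unless medical care requires otherwise. Section 10.1.1 says that the primary analysis is unblinded, but not when or by whom.

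On access to the codes, section 5.5 has the protocol biostatistician make the assignment list and deliver it to the Research Pharmacy. Other unnamed key staff may receive it if required.

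On oversight:
- Section 9.5 lists "monitoring clinical trial efficacy endpoints" among the PI's responsibilities. It also states: "The SKCCC Safety Monitoring Committee will review all trial monitoring and reporting annually".
- Section 9.7 brings together the PI, coordinators and, as appropriate, sub-investigators and biostatisticians. The topics end with "adherence to the protocol (i.e., potential or real protocol deviations/violations), completeness of data collection, and progress of data analysis".
- Section 9.8 states: "The principal investigator will have sole responsibility for monitoring and oversight of problems/events related to this research".

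**The concern.** Two instructions in the same plan do not fit together. One calls for comparisons by arm during enrolment. The other sets a single point at which staff are unblinded for analysis, after enrolment and Day 90 follow-up are complete. Someone who followed 5.6 to the letter would leave the first two rows of Table 5 unused. Someone who ran the looks would find no rule on who may see the result, and the nearest text, in 9.5, points to the PI.

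The primary outcome is a pain score that the patient gives, and 5.6 itself justifies blinding by the risk of bias in subjective outcomes. If the people who recruit and manage patients learned that one arm was ahead, their conduct of the rest of the trial could change. The final report could not rule that out, because the plan describes no barrier.

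**Working it through.** **Inputs from the documents.** Total 70 patients, 35 per arm (section 1). Looks at 28 and 42 (10.4). All patients through Day 90 in 24 months (10.3). Accrual period two years (section 1). Difference 1.5, SD 2.5, two-sided 0.05 (10.3). Boundaries 3.36, 2.68 and 1.98 (Table 5).

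**Assumptions.** Even accrual, surgery at enrolment, and 90 days = 90/30.44 = 2.96 months.

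**1. The plan's own figures.** 28/70 = 0.40 and 42/70 = 0.60, as stated. The Lan-DeMets spending function of O'Brien-Fleming type, 4 − 4Φ(z(1 − 0.05/4)/√t), gives cumulative alpha 0.00079, 0.0076 and 0.0500 at t = 0.4, 0.6 and 1.0. The matching critical values are 3.357, 2.680 and 1.981. Table 5 reproduces, and its alpha column is cumulative. The problem is therefore not in the boundaries.

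**2. Time between each look and permitted unblinding.** The two statements of duration allow two readings.

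| | Last Day 90 visit at month 24 | Accrual itself takes 24 months |
|---|---|---|
| Accrual | 24 − 2.96 = 21.04 months | 24 months |
| Last Day 90 visit | month 24 | 24 + 2.96 = month 26.96 |
| Look 1 (0.4 × accrual) | month 8.4 | month 9.6 |
| Look 2 (0.6 × accrual) | month 12.6 | month 14.4 |
| Gap from look 1 | 15.6 months | 17.4 months |
| Gap from look 2 | 11.4 months | 12.6 months |

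The range is about 11 to 17 months. If the looks waited for 5.6, all 70 patients would already be enrolled and only one analysis would remain.

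**3. Patients enrolled after each look.** 70 − 28 = 42 (60%) and 70 − 42 = 28 (40%).

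**4. Could a look call for action?** At the plan's difference and SD, the expected final Z is 1.5/(2.5 × √(2/35)) = 2.51. At look 1 it is 2.51 × √0.4 = 1.59, and the chance of passing 3.36 is 1 − Φ(1.77), about 4%. Recursive numerical integration gives a cumulative chance of about 23% by look 2. This uses the normal approximation for a comparison of means. A crossing is realistic enough that someone must be named to act on it.

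**5. What the plan assigns.**

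| Question | What the documents give |
|---|---|
| Who can hold the codes? | Protocol biostatistician, Research Pharmacy, unnamed others if required (5.5) |
| Who runs the looks? | Not stated |
| Who receives the results? | Not stated; 9.5 gives the PI efficacy endpoints in general terms |
| Who decides what follows a crossing? | Not stated |
| How is the team shielded? | Not stated; biostatisticians may sit in the 9.7 meetings with the PI |

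**The case against.** The best reply is that nothing here is impossible. Section 5.6 speaks of study staff, and 5.5 shows that the biostatistician who makes the list needs no unblinding. That person could run both tests and report only whether a boundary was crossed. This stands. A reader might infer that the looks either cannot happen or must reveal arm results to the team; the documents do not force that choice. They simply do not assign the task.

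Other strong readings also go too far:
- **That the plan sends interim results to the PI.** No passage routes them to anyone. The efficacy duty in 9.5 does not say by arm, and 9.7 lists progress of analysis, not results.
- **That the PI is the only overseer.** Section 9.8 concerns problems and events. Section 9.5 also names quality audits, the annual committee review, the IRB and a trial monitoring review group.
- **That the PI is expressly blinded.** Section 5.1 names the anesthesiologist, the surgeon and the patient. The PI's blinding is inferred from 5.6 and 5.7.
- **That nobody can see harm by arm during accrual.** Section 9.5 says: "The PI will constantly review the safety reports to confirm that the safety outcomes favor continuation of the study". It does not say by arm, and the cancer center's monitoring plan that it cites is not among these documents.

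The reply also notes that an aggregate result reveals no patient's assignment, that postoperative assessors are blinded and that postoperative orders are standard. This limits the route to biased scoring. It does not remove the effect on recruitment or on decisions about the trial.

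**Conclusion.** The concern holds as a conflict between 10.4 and 5.6 together with a missing process, and it should be settled before the first look. The looks need codes about 11 to 17 months before the only stated unblinding for analysis. That range rests on even accrual and covers both readings of the 24-month figure. It measures calendar time, not bias. The 42 and 28 patients are those whose enrolment follows each look and who would be exposed if results leaked. They are not an estimate of harm, and the documents give no basis for one. The verdict does not depend on the PI being blinded, on 9.8, or on any claim about safety review by arm.

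**What to change.** 1. **Section 5.6:** add an exception for the two interim looks. A statistician who holds the assignments and has no patient contact runs the Table 5 tests.
2. **Section 10.4:** name that statistician's role and a recipient outside the conduct team. The SKCCC Safety Monitoring Committee is a candidate if its remit allows; the documents do not show whether it reviews efficacy boundaries. Only a continue or stop recommendation goes to the PI.
3. **Sections 9.5 and 9.7:** state that the PI and the study meetings see only pooled, blinded data before the final unblinding.

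An adverse-event table by arm in the same report is optional, and the point does not need it.

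The cost is protocol wording and two short reports timed by enrolment instead of the annual review. If the committee's remit does not cover efficacy, another recipient must be found. No patients or procedures are added, and Table 5 is unchanged.
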